## **1.0 Objectives / Specific Aims:**

[figure not shown]
Sinusonic is a simple handheld device that uses acoustic vibrations (128Hz) and positive expiratory pressure as patients exhale through their nose. Beneficial effects have been shown in a clinical trial studying chronic rhinitis that showed improvements in nasal blockage/congestion, nasal drainage, nasal/sinus pressure and sense of smell (Soler ZM et al available at <https://onlinelibrary.wiley.com/doi/full/10.1002/alr.22537>). A small unpublished pilot study demonstrated >70% increases in peak nasal nitric oxide (NO) after one use of Sinusonic. NO is known to stimulate mucociliary clearance and has antiviral properties. Given that Sinusonic improves nasal congestion, nasal drainage and appears to increase NO which has antiviral properties, our hypothesis is that use of Sinusonic will decrease the frequency, severity and duration of community acquired viral URIs.

Aim 1: To determine if Sinusonic decreases the number of URIs experienced during an 8 week fall URI season. Subjects will use an active device (positive expiratory pressure and 128 Hz) or a sham device (no positive expiratory pressure and 1,000 Hz) for 1 min three times a day for 8 weeks. Daily URI symptoms will be recorded electronically.

Aim 2: To determine if Sinusonic decreases the severity and duration of community acquired viral URIs. Subjects will use active or sham device as above. Severity and duration of URIs will be recorded using daily symptom diaries.

## 2.0 Background

Sinusonic is a simple handheld device that uses acoustic vibrations (128Hz) and positive expiratory pressure as patients exhale through their nose. Beneficial effects have been shown in a clinical trial that showed improvements in nasal blockage/congestion, nasal drainage, nasal/sinus pressure and sense of smell (Soler ZM, et al).

Some of these benefits occurred after one use of the device and these benefits continued to increase throughout the 5 week study. In this clinical trial, approximately 80% of patients demonstrated improvement. A small unpublished pilot study demonstrated >70% increases in peak nasal NO after one use of Sinusonic. Our hypothesis is that use of Sinusonic improves nasal congestion, mucociliary clearance and exhaled NO, all of which decrease viral infections.

## 3.0 Intervention to be studied

Subjects will be screened for likely inclusion during the summer months. Baseline demographics, medical comorbidities, and URI symptoms will be assessed. Informed consent will be completed.

The fall URI season typically runs through September and October (Turner R et al). Towards the end of screening, all subjects will be randomized 2:1 to active use of Sinusonic (128Hz) for 1 minute 3 times daily or an identical “placebo” device that emits a frequency of 1,000 Hz and has the ball valve modified to eliminate positive expiratory pressure. Devices will be shipped to home addresses via overnight mail. On September 1, 2020 all subjects will begin daily use of their assigned device. Subjects will remain blinded as to treatment arm until study completion.

Subjects will be asked to complete a brief daily questionnaire on URI symptoms and whether or not they feel as if they have a “cold”. Previously validated questions for viral URI studies are rating 8 items on a likert scale from 0 (no symptoms) to 3 (severe symptoms) (Jackson GG, et al). The 8 symptoms are: sneezing, runny nose, nasal obstruction, sore throat, cough, headache, malaise, and chilliness. A Total Symptom Score (TSS) will be the sum of each symptom to provide a daily score ranging from 0 to 24. Prior studies have defined the common cold as present when:

- 1)  $TSS \geq 14$  PLUS moderate or severe nasal discharge x 3 days OR patient subjective impression they have a cold OR

2) TSS < 14 AND moderate or severe nasal discharge x 3 days AND subjective impression they have a cold

Answers will be uploaded to secure REDCAP database. The study duration is 8 weeks. At the end of the study, subjects will be asked questions regarding device safety and tolerability.

Our primary outcome will be absolute number of URIs experienced during the 8 week study period. Secondary outcomes will be time to first URI, duration and symptom severity of viral URIs. These metrics will allow us to determine if Sinusonic decreases the frequency of URIs, as well as potentially shortening the duration or decreasing the severity of URIs.

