## 10.0 Data Management

All analyses and graphs will be performed with SPSS 24.0, Sample Power 3.0, and Sigma Plot 10.0 (SPSS, Chicago, IL.). Disease information and demographic variables, such as age, gender, race, and VAS scores will be summarized using frequencies, means, and standard deviation as appropriate. Our primary outcome metric is number of viral URIs as defined above. Secondary outcome metrics include average duration of URIs and severity of symptoms (as measured by TSS) of URIs. Categorical variables will be compared using Chi Square or McNemar's test. Continuous variables will be compared using One-Way ANOVA with repeated measures follow by post-hoc analysis. Data regarding safety and patient satisfaction will be summarized for each time point. A p-value  $\leq 0.05$  will be considered statistically significant. Due to the exploratory nature of this study, no p-value correction (ie Bonferroni) will be applied.

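### Colds still open when the 8-week diary closes have no recorded end and no analysis rule, so average URI duration (Aim 2) is understated and a true arm difference shrinks

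*Combined protocol and SAP*

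**What the plan says.** Section 1.0 (Aim 2) names the only source of the outcome: "Severity and duration of URIs will be recorded using daily symptom diaries". Section 3.0 sets a common start, "On September 1, 2020 all subjects will begin daily use of their assigned device", a common length, "Answers will be uploaded to secure REDCAP database. The study duration is 8 weeks", and a season: "The fall URI season typically runs through September and October". The primary outcome uses the same window: "Our primary outcome will be absolute number of URIs experienced during the 8 week study period".

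Section 10.0 gives the duration outcome and its method: "Secondary outcome metrics include average duration of URIs and severity of symptoms (as measured by TSS) of URIs", and "Continuous variables will be compared using One-Way ANOVA with repeated measures follow by post-hoc analysis".

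The schedule in Section 9.1 has no column after the study endpoint, and Section 6.0 puts the last collection of follow-up measures at 8 weeks. Section 11.0 allows observation beyond the last timepoint, but only to follow adverse events. It does not mention the diary, the TSS or URI duration. No section says when an episode ends for the duration outcome, or what happens to one still open on the last day.

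**The concern.** A cold that starts shortly before the diary closes has an onset but no observed end, so its true length is unknown. The plan offers no way to use that partial information. ANOVA needs one finished number per cold, so the analyst must either enter the truncated length or leave the cold out. Both choices push the mean down when durations vary, because long colds are more likely to be open at a fixed date and lose more days when they are.

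Aim 2 asks whether the device shortens colds. The arm with longer colds loses more recorded days, so a real difference is reported as smaller than it is and the comparison loses power. The missing end dates cannot be recovered once the diary has closed.

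**Working it through.** **Inputs from the documents**
- Start 1 September 2020, 8 weeks = 56 days (Section 3.0). Day 30 is 30 September, so day 56 is 26 October, 5 days before the end of the stated season.
- 100 sham and 200 active subjects, URI rates 50% and 33% (Section 5.0).

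**The plan's own figure.** Section 5.0 states neither power nor sidedness; two-sided 0.05 is assumed. The pooled rate is (50 + 66)/300 = 0.387. The null SE is √(0.387 × 0.613 × (1/100 + 1/200)) = 0.0596. The alternative SE is √(0.25/100 + 0.2211/200) = 0.0600. Power is Φ((0.17 − 1.96 × 0.0596)/0.0600) = about 81%, so the design reproduces at roughly 80% power. This point does not change N. Expected subjects with a URI: 0.50 × 100 + 0.33 × 200 = 116.

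**Assumptions.** One cold per subject with a URI; onset day uniform on days 1 to 56; mean durations of 7, 10 or 14 days, shown as a range because the documents give none.

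**Fixed duration D, daily diary, T = 56.** A cold is cut if it starts on one of the last D − 1 days, and those colds lose 1, 2, …, D − 1 days. Hence share open = (D − 1)/T, and recorded mean = D − D(D − 1)/(2T).

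| D | Share open | Open colds of 116 | Recorded mean if kept | Bias |
|---|---|---|---|---|
| 7 | 6/56 = 10.7% | 12.4 | 7 − 42/112 = 6.63 | −5.4% |
| 10 | 9/56 = 16.1% | 18.6 | 10 − 90/112 = 9.20 | −8.0% |
| 14 | 13/56 = 23.2% | 26.9 | 14 − 182/112 = 12.38 | −11.6% |

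**Durations that vary.** Simulation with gamma durations, CV 0.5, rounded to whole days, T = 56:

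| Mean | Recorded mean if kept | Bias | Mean if open colds dropped | Bias | Bias if kept, longest quarter | Bias if kept, shortest quarter |
|---|---|---|---|---|---|---|
| 7 | 6.52 | −6.9% | 6.76 | −3.5% | −9.9% | −2.2% |
| 10 | 8.98 | −10.3% | 9.47 | −5.4% | −14.8% | −3.6% |
| 14 | 11.94 | −14.7% | 12.86 | −8.2% | −20.9% | −5.6% |

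If every cold had the same length, dropping open ones would cause no bias. The bias from dropping arises because durations differ.

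**Effect on an arm difference.** A true 10 versus 7 days (3.0 days) is recorded as 9.20 − 6.63 = 2.57 days with fixed durations kept at cut-off length, 8.98 − 6.52 = 2.46 days at CV 0.5, and 9.47 − 6.76 = 2.71 days if open colds are dropped at CV 0.5. A true 10 versus 8 days (CV 0.5) is recorded as about 1.6 days if kept and 1.8 if dropped.

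**Effect on power.** For 10 versus 8 days with 50 sham and 66 active colds at CV 0.5, power with full durations is about Φ(2/√(5²/50 + 4²/66) − 1.96) = Φ(0.36) = 64%. Simulation gives about 66% with full durations and 51% with truncated ones.

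**Sensitivity to the window.** Section 9.1 puts study start at 12 days and the endpoint at 60 days, 48 days apart rather than 56. Sixty days counted from 1 September would end on 30 October, still in season. Over windows of 48 to 60 days, means of 7 to 14 days and CV 0 to 0.5, the bias with open colds kept runs from about −5% to −17%.

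**The case against.** The strongest reply is that this is a secondary outcome in a study described as a pilot and as exploratory, that both arms share the same cut-off, and that the result is mainly conservative. That is fair as to weight. With equal durations and onset timing in the two arms, truncation creates no false difference. It does not remove the loss: Aim 2 would still be answered with a shrunken difference and less power.

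The documents do not say in words that the diary stops at week 8. That is an inference from the stated duration, the 8-week last collection and the absence of any later diary. It is a strong inference, since nothing points the other way.

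The season overrun is short. Section 1.0 itself speaks of an 8-week fall URI season, and the gap to 31 October is 5 days, or 1 day on the 60-day count. The argument does not depend on it: truncation needs only that some colds start near the end.

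A reader might infer several stronger things that the documents do not support:
- That open colds will be entered as if they had resolved. The plan states no handling, and dropping them gives a smaller bias.
- That severity is understated too. A summed TSS would be too low, but a mean or peak TSS has no fixed direction, and Section 10.0 does not say which is meant.
- That late colds cannot count as URIs because three days of discharge are required. On one reading of criterion 1 in Section 3.0, a subject's own impression of a cold is an alternative route.
- That a device which delays onset would produce a spurious shortening of note. With active onsets kept out of the first 7 days and equal true durations (mean 8 or 10 days, CV 0.5), the false difference was only about 0.1 day and false positives stayed at about 5% to 6%.

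**Conclusion.** The point holds for URI duration. A fixed diary window, an average compared by ANOVA and no rule for open episodes together understate duration when durations vary, whether open colds are kept or dropped. For assumed 7- to 10-day colds with uniform onsets, about 11% to 16% would be open at the end. The understatement is about 5% to 8% if they are kept (7% to 10% at CV 0.5) and 3.5% to 5.4% if they are dropped at CV 0.5. With open colds kept, a true 3-day difference is recorded as about 2.6 days or less.

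The bias is moderate, its direction for the comparison is toward no difference, and its size rests on assumed durations. The effect on the primary count is small, and no direction is claimed for severity. It should be corrected because Aim 2 depends on this outcome and the remedy is cheap; it does not threaten the primary analysis or the sample size.

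**What to change.** **Sections 3.0 and 9.1.** Keep the 8-week window for URI onset. Let any subject with an open episode on the last day continue the same evening REDCap diary until the episode ends, up to a stated cap (for example 14 days). Keep blinding until that diary closes. State the diary-based rule that ends an episode, since without it neither the extension nor the outcome can be applied. Record whether the device was used on the extra days so that they can be identified in the analysis. Reconcile the day counts in Section 9.1 with the 8 weeks in Section 3.0.

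**Section 10.0.** Replace ANOVA on recorded lengths with a method that treats episodes still open at the cap, or at loss to follow-up, as censored, for example Kaplan-Meier with a log-rank or Cox comparison. If the diary is not extended, apply the same censoring at the last diary day.

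**Cost.** Database lock moves by about two weeks, and roughly 12 to 19 subjects (for 7- to 10-day colds) complete extra diary days. N = 300 and the primary outcome's onset window are unchanged, and no new subjects, staff or procedures are needed.

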### 3.1 Device Instructions

Instructions for use:

1. Hold the SinuSonic device at a 45-degree angle
2. Deep breathe in through mouth
3. Hold the SinuSonic to your nose and blow out into the mask of the SinuSonic. The goal here is to hear the “target flutter” sound that is desired during treatment with the SinuSonic
4. You will feel a little resistance to breathe out and a vibration sensation from a speaker in the device
5. Remove the device to “blow the nose” if nasal drainage occurs
6. Return the device to the nose then breathe in and out thru the nose to try and hear the “target flutter” sound
7. Time of use is 1 minute of nasal breathing with the device - as tolerated
8. Goal is to use Sinusonic 3 times per day with uses separated by at least 5 minutes.

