### 3.2 Device Usage and Safety

The SinuSonic consists of a fully-disposable medical grade silicone nosepiece mounted to a resin body. The device is equipped with a flutter valve located at the top of the device which creates gentle, self-guided oscillating expiratory resistance.

The SinuSonic is a legally marketed device used in accordance with its labeling. It is substantially equivalent to many Class I OTC devices with the same intended use and indications for use in clearing mucus to improve air flow, such as the Navage Nose Cleaner.

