### Exclusion Criteria

Any transient ENT condition that may impact upper airway to include acute sinusitis or otitis.

Any upper respiratory illness within last 2 weeks

TSS will be measured at baseline as described above and must be <9 for inclusion (Eccles etal).

Topical decongestant use in last week

Current nasal crusting or history of ulceration or perforation

History of severe nose bleeding within last 3 months

Known pregnancy

Immunosuppressed condition or on immune modulating medications such as prednisone or chemotherapy

Allergic sensitivity to silicone or any other component of device

Inability to read and understand English

Inability to perform treatment due to underlying medical condition

After confirming that subjects meet inclusion criteria, they will be entered into study as outlined below. Subjects who have URI symptoms at the beginning of the study will specifically be excluded, as the purpose of the study is prevention of URIs, not treatment of pre-existing URIs.

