#### **7.0 Recruitment Methods**

We will publicize the study through MUSC and Sinusonic social media targeting geographic regions described above. A number and email will be provided for subjects interested in participating. Only one subject per household can be enrolled.

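### The device instructions promise a resistance the sham is built to lack, and nobody is asked about prior SinuSonic use: a cheap gap to close, of unknown and probably small effect

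*Combined protocol and SAP*

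**What the plan says.** Section 3.1 gives one set of device instructions. Step 4 says "You will feel a little resistance to breathe out", along with a vibration from a speaker. Steps 3 and 6 direct the user to listen for a target flutter sound. Section 3.2 explains where the resistance comes from: "The device is equipped with a flutter valve located at the top of the device which creates gentle, self-guided oscillating expiratory resistance".

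The sham differs on exactly this feature. Section 3.0 says it "has the ball valve modified to eliminate positive expiratory pressure" and emits 1,000 Hz instead of 128 Hz; Section 1.0 describes it in the same way. Section 3.0 otherwise calls the placebo device identical and states: "Subjects will remain blinded as to treatment arm until study completion". No sham-specific or arm-neutral instructions appear, and nothing says who receives the Section 3.1 text.

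On access to the device, Section 3.2 says "The SinuSonic is a legally marketed device used in accordance with its labeling", and Section 7.0 says "We will publicize the study through MUSC and Sinusonic social media targeting geographic regions described above". The only eligibility criterion that touches on the device itself is "Allergic sensitivity to silicone or any other component of device". None of the eight Appendix screening questions, and no item on the baseline history, medication or comorbidity forms, asks about prior or current SinuSonic use. The daily diary asks only how many times Sinusonic was used in the last 24 hours.

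**The concern.** Every component of the primary outcome comes from the subject's own diary: the symptom scores, the severity of nasal discharge and the impression of having a cold. Section 3.0 describes no laboratory confirmation. Blinding is therefore the main protection against biased reporting.

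Two features of the plan put avoidable strain on it. First, if sham subjects receive the Section 3.1 text, they are told to expect a sensation their device was designed not to produce. Second, a person who has used a SinuSonic has a direct comparator for the sham, and one who owns a SinuSonic can go on using it.

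The two routes act in opposite directions. Sham subjects who recognise their arm and over-report colds would make the device look preventive. Sham subjects who use an active device would dilute a real effect. As written, the plan collects nothing that would let the analyst detect or examine either afterwards.

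**Working it through.** **1. Comparing the passages.** Section 3.1 step 4 promises resistance. Section 3.2 attributes resistance to the valve. Sections 1.0 and 3.0 say the sham's valve is altered so that there is no positive expiratory pressure. The mismatch is clear for resistance. It is not established for the other cues: the sham also emits a tone, so a vibration may still be felt, and the documents do not say whether the sham flutters.

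**2. The plan's own figure.** Section 5.0 gives 100 sham and 200 active subjects and a fall in URI proportion from 50% to 33%. Section 10.0 gives p ≤ 0.05. Two-sided testing is my assumption, and no power level is stated. For the pooled two-proportion z test:

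- Pooled rate = (100 × 0.50 + 200 × 0.33)/300 = 0.3867
- SE under the null = √[0.3867 × 0.6133 × (1/100 + 1/200)] = 0.0596
- SE under the alternative = √(0.50 × 0.50/100 + 0.33 × 0.67/200) = 0.0600
- Power = Φ[(0.17 − 1.96 × 0.0596)/0.0600] = Φ(0.88) = 81.2%

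Exact binomial enumeration of the same test gives 81.3%. The sample size is consistent with a conventional 80% target and is not in question here.

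**3. Illustration: over-reporting in the sham arm, no true effect.** Active rate 50%; sham rate 50% plus a gap. The table gives the probability of a significant result favouring the device.

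| Gap (points) | Exact | Normal approximation |
|---|---|---|
| 0 | 2.7% | 2.5% |
| 0.5 | 3.2% | 3.0% |
| 1 | 3.9% | 3.6% |
| 2 | 5.4% | 5.1% |
| 5 | 13.2% | 12.6% |

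To see what a gap requires: gap = 0.5 × r × s, where 0.5 is the share of sham subjects otherwise without a URI, r is the share who recognise their arm, and s is the share of those who then report a URI they would not otherwise have reported. With s = 0.2:

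- r = 0.05: 0.5 × 0.05 × 0.2 = 0.5 point
- r = 0.10: 0.5 × 0.10 × 0.2 = 1 point
- r = 0.20: 0.5 × 0.20 × 0.2 = 2 points
- r = 0.50: 0.5 × 0.50 × 0.2 = 5 points

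**4. Illustration: sham subjects using an active device, true rates 50% and 33%.** If a share c of sham subjects gets the full active effect, the sham rate is 0.50 − c × 0.17.

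| c | Sham rate | Exact power |
|---|---|---|
| 0 | 50.00% | 81.3% |
| 1% | 49.83% | 80.5% |
| 2% | 49.66% | 79.7% |
| 5% | 49.15% | 77.3% |

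The arm sizes and the 50% and 33% rates come from Section 5.0. Every level of gap, r, s and c is assumed. The calculation uses the proportion with a URI, as Section 5.0 does, although the stated primary outcome is the number of URIs.

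**The case against.** The strongest reply is that no loss of blinding is demonstrated, and that is correct. A reader might infer from step 4 that sham subjects will discover their arm. The documents do not support this. They do not say that sham subjects receive the Section 3.1 text; the cue is mild; a subject new to the device has nothing to compare it with; and the sham still emits a tone. Consent material is not available for review, so other participant-facing wording cannot be checked.

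Nor does any passage show that enrolled subjects will own a SinuSonic. That possibility is inferred from marketing status and the recruitment channel. Section 16.0 gives every participant a free device, so buying one during the study is less likely and prior ownership is the main route.

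A false URI is also not always easy to produce. The second limb of the Section 3.0 definition requires three days of moderate or severe discharge as well as a felt cold. The first limb can be read either as requiring a total score of at least 14 in every case or as satisfied by a felt cold alone, so the scope for over-reporting depends on which reading is used.

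Finally, Section 9.0 calls the study a pilot and Section 10.0 calls it exploratory. Section 10.0 plans no adherence-based analysis and Section 18.0 adds weekly compliance calls, so counting use of a personal device as adherence would have little consequence.

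These points limit the severity. They do not answer the narrower point: prior users can be enrolled without anyone knowing, and if prior use is not recorded, no sensitivity analysis can be done later.

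**Conclusion.** The point holds as a low-severity, inexpensive improvement. The only documented instructions promise a sensation the sham is built to lack, the text given to sham subjects is unspecified, and prior or current use of a marketed device is never asked about although the product's own social media is a recruitment channel.

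The size of the risk is unknown. At low levels it is small: 1 to 2 points of sham over-reporting adds about 1.2 to 2.7 percentage points to the one-directional false-positive probability (3.9 − 2.7 and 5.4 − 2.7), and 1–2% crossover costs about 0.8 to 1.6 points of power (81.3 − 80.5 and 81.3 − 79.7). A reader might take the 13.2% figure as the expected harm. It is not: under the assumptions shown it needs half of all sham subjects to recognise their arm, and nothing in the documents supports that level.

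The conclusion rests on the outcome being self-reported and on the change being cheap. It does not rest on any evidence that unblinding would occur.

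**What to change.** 1. Add one question to the Appendix screening or baseline form, such as *Have you ever owned or used a SinuSonic?* Prespecify in Section 10.0 a sensitivity analysis of the primary comparison that omits prior users. Excluding prior users in Section 4.0 is optional and is the sponsor's choice; recording them avoids narrowing eligibility.

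2. Reconcile Section 3.1 with Sections 1.0 and 3.0. State that both arms receive the same text, and word step 4 so that it does not promise a sensation the sham lacks. Steps 3 and 6 need more care, because the target flutter works as feedback on technique and is not mere description. The sponsor should confirm whether the sham still flutters before changing them. The manner and frequency of use stay as they are. Because Section 3.2 says the device is used in accordance with its labeling, the sponsor should also check the revised text against that labeling.

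3. Optionally, have the daily use item refer to *your study device*, so that use of a personally owned device is not counted with it.

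The cost is one extra question, one small extra analysis and the loss of one descriptive cue for active users. Sample size and the main analysis do not change.
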